Test Up Now Education Program

NCT04304001

Document Date: 1/26/2022

Study Protocol and Statistical Analysis

Study Protocol

The TUNE-UP study is designed as a two-group pretest/posttest pragmatic randomized controlled trial. The study uses the parallel group, two arm superiority trial design with 1:1 allocation ratio. The pragmatic trial aims to test the effectiveness of the intervention in the setting of community health centers. To conduct the intervention trial, 115 participants were randomized at the time of enrollment following completion of the baseline survey. The two experimental arms are: 1) an intervention group which receives the adapted Screen to Save (S2S) educational materials, a tailored brochure for African Americans on colorectal cancer (CRC) screening with input from focus group research, and CHA in-person and cellphone education and counseling supplemented by text messages; and 2) a control group which receives the brochure only. Participants in both study arms received communication from their CHC to receive their stool-based testing kit. The primary outcome is CRC screening by 12-months post-intervention (i.e., receipt of the stool-based test). The intermediary CRC screening outcome is measured at 3-months. Secondary outcomes included CRC knowledge and CRC screening self-efficacy.

Study participants and setting

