All statistical analyses were performed using SAS 9.4. First, summary statistics were generated for all variables. Then bivariate analyses were conducted for key variables to compare differences between the intervention and control arms. Proportions calculated from categorical variables were compared using a chi-square test; means obtained continuous variables were compared using two-sample t-test. The multivariate analyses were conducted using the GEE procedure in SAS that implements the generalized estimating equations regression. Analyses were performed using an intent-to-treat approach that includes all participants randomized. Significance tests were two-sided and employed an overall significance level of $\alpha=0.05$. For each arm, the proportion of participants who receive CRC screening by 12 months was computed. The chi-square test was used to compare the two treatment arms for screening receipt. If the proportion of participants receiving CRC screening in the intervention arm is at least 15% higher than that in the control arm, the intervention will be determined to be effective. In addition, since our sample size gets small when participants are stratified by community health center or sex, we will use Fisher's exact test to assess the effect of the intervention. To assess the influence of key covariates (age, income, marital status, education, insurance status) on the primary outcome, logistic regression analysis was employed. In addition, to investigate treatment effects over time (baseline, 3 months, and 12 months), we will estimate hazard ratios by fitting Cox proportional models using time-varying covariates. In these models, the receipt of CRC screening will be regressed at each actual time point on time elapsed since baseline to test for an interaction between time and treatment group. The basic model will be repeated, adjusting for age, income, marital status, education, and any other significant covariates at baseline. To test the proportional hazard assumption, the Kaplan-Meier curve and the Schoenfeld residuals will be used for fixed and time-varying covariates, respectively.

Mediation and moderation analyses will be conducted to determine why and when variables are related, respectively. We will focus on specific mediators to include CRC perceived susceptibility, CRC self-efficacy, and CRC knowledge in the conceptual model.

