The complexities of the relationships between the exogenous variables (X) and the endogenous variables (Y) as a function of the mediators will be examined using three separate regression models. We will ensure that the assumptions of continuous measurements (i.e., that all variables are measured on a continuous scale), normality (i.e., normal distribution of all variables), independence (i.e., that there is no correlation of errors from one observation to another observation), and linearity (i.e., evidence linear relationships among the variables) are met. We will assess direct causality and indirect causality using standardized regression coefficients (i.e., betas) to determine the direction and magnitude of the effect of one variable upon the other variable.

We will confirm that the mediators (i.e., CRC perceived susceptibility, CRC self-efficacy, and CRC knowledge) are caused by the exogenous variables X and are also the causes of the endogenous variables Y. We will also determine if X loses its significance when M is included in the model. Specifically, we will perform regression analyses and confirm the significance of the relationship between the exogenous (i.e., independent variable - IV) and endogenous variables (i.e., dependent variable - DV), the exogenous and mediator variable, the mediator and the endogenous variables in the presence of the IV, and lastly, we will confirm the lack of significance (or the meaningful reduction in effect) of the relationship between X and Y in the presence of the mediators.

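### The mediation rules read the mediator-to-screening path as causal given arm alone, with no baseline adjustment specified, and so can produce false mediators

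*Combined protocol and SAP*

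**What the plan says.** The design is a "two-group pretest/posttest pragmatic randomized controlled trial", and "115 participants were randomized at the time of enrollment following completion of the baseline survey". Knowledge and self-efficacy are listed as secondary outcomes; perceived susceptibility is not.

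Statistical analysis gives two mediation rules for these three candidates.

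- **Stepwise rule** (the paragraphs on three regression models). It tests arm to screening, arm to mediator, and mediator to screening with arm in the model. It then looks for loss of significance, or a meaningful reduction, of the arm effect once the mediator is added. The aim is to confirm that mediators "are caused by the exogenous variables X and are also the causes of the endogenous variables Y", and the plan adds: "We will assess direct causality and indirect causality using standardized regression coefficients".
- **Baron and Kenny rule** (the last paragraph on mediation). A candidate is a mediator if arm is significant, the candidate is significant, and the arm coefficient shrinks.

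Neither rule names a baseline mediator score, a covariate or a sensitivity analysis. The assumptions to be checked are continuity, normality, independence and linearity; absence of mediator-outcome confounding is not among them. The opening paragraph of the same section does name covariates (age, education, income, marital status; insurance as well for the logistic model), but for the logistic and Cox models only.

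**The concern.** Randomization protects the comparison of arms on the mediator and on screening. It does not protect the comparison of people with high and low mediator scores within an arm. Someone who starts with more knowledge, confidence or education may score higher later and also screen more, whatever the mediator does. A model with arm and the follow-up score alone credits that difference to the mediator. Measuring the mediator before screening does not remove the problem.

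At stake is the explanatory claim. A stable personal trait could be reported as the mechanism through which the community health advisor programme works, with the direct effect of arm understated.

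**Working it through.** The plan gives no error rate, control screening rate or effect size for mediation, so there is no figure to reproduce. The check is a simulation.

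**From the documents:** 115 randomized 1:1 (58/57); two-sided 0.05; binary screening outcome; the two rules above.

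**Assumed:** the mediator has no effect on screening. M0 is the baseline mediator score, M1 its follow-up value, r their within-arm correlation and g the log-odds of screening per SD of M0.

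- M1 = r × M0 + 0.5 × arm + noise, scaled to unit variance within arm
- logit P(screen) = −0.85 + 0.65 × arm + g × M0

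At the average M0, control screening is 1/(1 + e^0.85) = 0.299 and intervention screening is 1/(1 + e^0.20) = 0.450, a difference of about 15 points. Outcome models are logistic. There were 2,500 trials per setting.

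| (r, g) | (0.4, 0.5) | (0.5, 0.7) | (0.6, 0.7) | (0.7, 0.9) |
|---|---|---|---|---|
| Mediator significant given arm | 15% | 36% | 49% | 81% |
| Same, M0 in the model | 5% | 4% | 5% | 5% |
| Arm-to-mediator and mediator-to-screening both significant | 11% | 27% | 37% | 61% |
| False verdict, Baron and Kenny rule | 4% | 12% | 16% | 25% |
| False verdict, stepwise rule, any reduction counted | 3% | 9% | 13% | 21% |
| False verdict, stepwise rule, loss of significance required | 2% | 6% | 9% | 15–16% |
| Mean direct log-odds of arm (true 0.65) | 0.53 | 0.46 | 0.42 | 0.32 |

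Repeat runs agree to within about two percentage points. With no confounding (g = 0) the mediator path is significant in about 4% of trials. With M0 in the models, the Baron and Kenny verdict rate is about 1% and the mean direct effect is 0.67 to 0.69.

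**Why the verdict rates lie below the path rates.** Both rules also require a significant arm effect, which occurs in only 32% to 35% of these trials.

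**Direct effect.** Part of its fall reflects non-collapsibility of the odds ratio, not confounding. At g = 0.9, leaving out M0 alone would give about 0.65/√(1 + 0.346 × 0.81) = 0.65/1.13 = 0.57. The rest of the drop to 0.32 comes from conditioning on the confounded mediator.

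**Second data model.** Here a measured confounder affects M0, M1 and screening, and 'meaningful reduction' in the stepwise rule is taken as at least 10%.

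- The path is falsely significant in about 25–28%, 69–75% and 93–95% of trials at odds ratios of 1.5, 2.2 and 3.3 per SD. With adjustment for M0 and the confounder it is 4.0–5.7%.
- When arm moves the mediator by 0.5 to 0.8 SD, false Baron and Kenny verdicts are 9–26% for an arm effect of about 16 points and 23–79% for about 36 points.
- When arm does not move the mediator, the stepwise rule gives at most 1.3%. The Baron and Kenny rule, which has no arm-to-mediator test, gives 3–12%.

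**The case against.** The case on the other side has real force on five points.

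- **Verdict rate.** A reader might infer a false-mediator rate of 11% to 61% from the two component paths. The documents do not support that: both rules also need a significant arm effect, and its reduction once the mediator is added. The full-rule rates are the right ones. Even so, the plan says mediation analysis is informative about each covariate whether or not the intervention works, so the inflated path may be interpreted by itself.
- **Certainty.** A reader might infer that false mediators will arise. The documents give no confounding strength, and without confounding there is no inflation. The word is *can*.
- **Adjusted rates.** Their return to nominal is built in, because every confounder in the simulations is measured and adjusted for. This does not show that adjustment would remove all confounding in this trial.
- **Baseline scores.** A reader might infer that the trial holds baseline values for all three mediators. The contents of the baseline survey are not listed. The inference is reasonable for knowledge and self-efficacy; for perceived susceptibility it is undocumented.
- **Model content.** No mediation equation is written out, so it cannot be said that covariates are excluded. What stands is that none is specified here, while covariates are named for other models in the same section.

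**Conclusion.** The concern holds in a conditional form. Followed as written, the rules can declare an inert mediator causal and bias the direct effect of arm. Under the assumed confounding, the mediator path is falsely significant in about 15% to 81% of trials, and a full false verdict occurs in about 4% to 25% (Baron and Kenny) or 2% to 15% (stepwise, loss of significance). The comparator is about 1% under the Baron and Kenny rule when the baseline mediator is adjusted for and is the only confounder. These sizes rest on assumed values of r, g and the arm effects; a larger arm effect raises the verdict rates.

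A reader might also infer that the trial's main conclusion is in doubt. It is not: the 12-month screening comparison is between randomized arms and does not use these models. This is a should-fix point on a secondary, explanatory analysis.

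**What to change.** In the mediation paragraphs of Statistical analysis:

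1. In every mediator model and outcome model, include the baseline value of that mediator where it was collected. Check the baseline survey for perceived susceptibility and state the result.
2. Add a short, fixed set of baseline covariates already named in the plan, such as age, sex, education, insurance and health literacy. Write the equations out.
3. Replace the language of confirming causes with estimation of direct and indirect effects, assuming no unmeasured mediator-outcome confounding.
4. Add one sensitivity analysis showing how much residual confounding would explain away the estimated indirect effect.

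The cost is SAP wording, a few model terms and a few degrees of freedom out of 115 participants. Unmeasured confounding is not removed, which is why items 3 and 4 are needed as well as the adjustment.

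### The last mediation check can be met by the arm effect becoming non-significant, which with 115 participants will often happen while most of the effect is still direct

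*Combined protocol and SAP*

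**What the plan says.** The mediators are knowledge, self-efficacy and perceived susceptibility. The mediation text in the Statistical analysis section lists four checks:

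1. arm (X) is related to outcome (Y);
2. arm is related to the mediator (M);
3. the mediator is related to the outcome with arm in the model;
4. finally, the team will "confirm the lack of significance (or the meaningful reduction in effect) of the relationship between X and Y in the presence of the mediators".

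Just before this list the plan says: "We will also determine if X loses its significance when M is included in the model". The alternative in brackets, a meaningful reduction, has no threshold. The section offers standardized coefficients but plans no interval or test for the indirect effect, the direct effect or the proportion mediated.

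Further on, the paragraph that invokes Baron and Kenny for the Likert-type items gives a different rule. There the arm indicator and the candidate covariate must be significant, and the arm coefficient need only be smaller than before in absolute value. Loss of significance is not required.

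**The concern.** A non-significant adjusted arm coefficient can arise in three ways: the direct effect is absent, it is present but was barely detectable to begin with, or adding the mediator has widened its standard error. The fourth check cannot tell these apart. In a trial of this size a significant total effect will often lie close to the threshold, so removing a modest part of it is enough to cross back.

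What is at stake is interpretation. The intervention combines education with a kit-instruction video, calls about receipt and completion of the kit, and text messages. Some of these could raise screening without changing knowledge, self-efficacy or perceived susceptibility. If a mostly direct effect is reported as explained by a mediator, the trial points to the wrong components.

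**Working it through.** **Inputs from the documents.** Sample size: "115 participants were randomized at the time of enrollment following completion of the baseline survey", in a "parallel group, two arm superiority trial design with 1:1 allocation ratio", so 57.5 per arm on average. Test level: "Significance tests were two-sided and employed an overall significance level of" 0.05. Outcome, binary: "The primary outcome is CRC screening by 12-months post-intervention". Effect of interest: the intervention proportion "is at least 15% higher than that in the control arm", read here as 15 percentage points.

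**Inputs not given, so assumed.** Control risk, true effect, arm-to-mediator shift and dropout (taken as none). The plan states no figure for this analysis, so there is none to reproduce.

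**Step 1: how near the threshold a significant result lies.** For an observed difference d with mean risk p, z = d / sqrt(p(1-p) x 2/57.5). If the standard error stays fixed, significance is lost once the mediator removes a share 1 - 1.96/z of the effect. With a control risk of 30%:

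| Observed difference | z | Share removed before significance is lost |
|---|---|---|
| 15 points | 0.15/0.0903 = 1.66 | not significant to begin with |
| 20 points | 0.20/0.0914 = 2.19 | about 10% |
| 25 points | 0.25/0.0922 = 2.71 | about 28% |
| 30 points | 0.30/0.0928 = 3.23 | about 39% |

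In every significant row, most of the effect is still direct when significance goes. Power for a true 15-point difference is 36-49% for control risks of 20-70%.

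**Step 2: widening of the standard error.** If arm shifts the mediator by a SD, then in a linear model with 1:1 allocation the arm coefficient's standard error is multiplied by about sqrt(1 + a²/4). That is 1.01 at a = 0.3, 1.03 at 0.5 and 1.08 at 0.8. The arm effect can therefore cross the threshold even if the mediator does nothing.

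**Step 3: simulation with logistic models.** n = 115; conditional total odds ratio 2.4; control risk 30% or 50%; a = 0.3 to 0.8. An odds ratio of 2.4 takes 30% to 1.029/2.029 = 51% and 50% to 2.4/3.4 = 71%. That is about 21 points, more than the plan's 15.

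| | 70% direct, 30% mediated | No mediation |
|---|---|---|
| Significance lost, given a significant total effect | about 36-50% | up to about 18% (at a = 0.8) |
| Significance lost, given checks 1-3 passed | about 49-73% | - |
| All four checks met (the last by non-significance), given a significant total effect | about 22-33% | about 0.2-2% |

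**Step 4: same question with a linear-risk model.** 20,000 trials per scenario, control risk 30%, 30% of the effect mediated, arm tested by least squares. Each cell shows loss given a significant total effect / loss given checks 1-3 passed.

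| True difference | a = 0.5 SD | a = 0.8 SD |
|---|---|---|
| 15 points | 46% / 64% | 51% / 77% |
| 20 points | 44% / 53% | 49% / 69% |
| 25 points | 36% / 41% | 44% / 56% |
| 30 points | 26% / 29% | 34% / 41% |

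A control risk of 50%, or logistic regression, gives similar figures. Over all these settings the ranges are about 26-52% and 29-80%. With no mediation, all four checks are met in about 1% of all trials or fewer.

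**Step 5: the later rule.** With no mediation the adjusted arm coefficient is smaller than the unadjusted one in about 50% of trials. The shrinkage condition taken alone is thus met by chance half the time, and it does not say how much is mediated.

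**The case against.** The strongest reply is that loss of significance is one of four joint conditions. A reader might infer from the logic of Step 2 that the plan would declare a mediator with no effect on screening in up to about 18% of trials with a significant total effect. The documents do not support that. The third check screens out nearly all such cases, and the full rule is met in about 2% or less. Likewise, the 36-50% in Step 3 is how often one condition is met, not how often the whole rule is met; that is 22-33%.

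A second reply is that at 30% mediated, mediation is real, so calling the variable a mediator is correct. The text never says complete or full mediation, and its bracketed alternative allows partial mediation. This also stands: a reader might infer that the plan commits itself to claiming complete mediation, and it does not.

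Third, the only sentence that spells out when the team will conclude that a variable is a mediator is in the later paragraph, and it needs no loss of significance. Its scope relative to the four checks is unclear, however, and it does not withdraw them.

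What survives is a point about size. Passing the first three checks does not protect the fourth: among trials that pass them, a mostly direct effect loses significance more often, not less. Nothing else in the plan would show the reader how much is direct.

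**Conclusion.** The concern holds as a matter of magnitude. The fourth check treats non-significance as support for mediation. With 115 participants, an effect that is 70% direct would meet all four checks in roughly a quarter to a third of trials with a significant total effect (22-33%). The consequence is overstatement of how much the mediator explains; a false finding of mediation where there is none stays rare.

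The percentages rest on assumed control risk, effect size and mediator shift, on a single mediator, and on no missing data, measurement error or mediator-outcome confounding. The qualitative result holds under both models. It is weakest for large effects with little mediation: at 30 points and a 20% indirect share, loss given a significant total effect is about 16-24%. This is a supporting analysis, and the primary chi-square comparison does not depend on it.

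**What to change.** In the four-check text, delete both statements that use loss or lack of significance as a criterion. In their place:

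- base the mediation conclusion on the estimated indirect effect with a 95% confidence interval, for example by bootstrap, on the risk-difference scale because the outcome is binary;
- report the direct effect with its 95% interval beside it;
- state that a non-significant direct effect will not be described as complete mediation;
- apply the same rule in the later Baron and Kenny paragraph, so that the section has one criterion.

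The cost is revised SAP wording and slightly more analysis; no new data are needed. The intervals will be wide. For 30% against 50% at 57.5 per arm, the half-width for the total effect alone is 1.96 x sqrt(0.21/57.5 + 0.25/57.5) = 17.5 points, before any widening from the mediator. Complete mediation could then rarely, if ever, be claimed, which is a fair reflection of what 115 participants can show.

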Additionally, we will assess the moderator variables (i.e., sex, health literacy, family history of cancer) to determine under what condition (i.e., when) a given predictor X/independent variable (IV) is related to an outcome Y/dependent variable (DV). We will assess whether the moderation effect is enhancing (i.e., that is, increasing the moderator would increase the effect of the predictor on the outcome), buffering (i.e., that is, increasing the moderator would decrease the effect of the predictor on the outcome), or antagonistic (i.e., where increasing the moderator would reverse the effect of the predictor on the outcome). We will apply hierarchical multiple regression to examine the effects of the moderating variable. We will assess the interaction effect between X and M and whether or not such an effect significantly predicts the occurrence of Y. All variables will be standardized to facilitate data interpretation and avoid multicollinearity. We will fit a regression model predicting the outcome from both the predictor and moderator variables. We will check that both the effect of the predictor and the effect of the moderator, as well as the model (R²) are statistically significant. Then, we will fit another regression model that includes the interaction effect of the first model and check for a statistically significant R² change and a statistically significant effect of the interaction term to determine if moderation is occurring (i.e., both are statistically significant).

Mediation analysis allows assessment of each covariate's impact on the primary outcome independent of whether the intervention's effect is significant; thus, adding to scientific understanding of the relevance of each. To examine the mediating effects on the primary outcome of each of the short items scored on a Likert-type scale, we will follow the strategy of Baron and Kenny. We will conclude that the candidate covariate is indeed a mediator of the effects of the intervention if: (1) the treatment group indicator is significant; and (2) the candidate covariate is significant, and the coefficient estimate of the treatment group indicator is smaller in absolute value than its counterpart in analysis.

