To assess the impact of candidate moderators, we will use Cox proportional hazard model and other appropriate survival analysis models to investigate the primary outcome on treatment group, each candidate moderator, and the interaction of treatment and each candidate moderator at each measurement time point.

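### Moderation is to be tested by two unranked procedures with different effect scales and decision rules, and one of them, read literally, could rule out a true reversal of effect

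*Combined protocol and SAP*

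**What the plan says.** The combined protocol and SAP describes moderation twice, both times under Statistical analysis.

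- **Moderator paragraph** (sex, health literacy, family history of cancer): "We will apply hierarchical multiple regression to examine the effects of the moderating variable". All variables are standardized. A first model holds predictor and moderator, and both effects and the model R² are checked for significance. The interaction is then added, and the analyst is to "check for a statistically significant R² change and a statistically significant effect of the interaction term". The result is to be labelled enhancing, buffering or antagonistic. The outcome is called Y and is not named, though the text speaks of its occurrence.
- **Last paragraph of the section**: for candidate moderators, "we will use Cox proportional hazard model and other appropriate survival analysis models to investigate the primary outcome", with a treatment-by-moderator interaction at each measurement time. No decision rule is given.

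The Study Protocol section makes the primary outcome receipt of a stool-based test by 12 months, a yes/no status. Fisher's exact tests within sex and health-center strata are also planned. Nothing says which analysis leads, which is supportive, or what is concluded if they differ.

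**The concern.** Interaction is not a property of the data alone; it depends on the scale of the effect. Linear regression of a yes/no outcome asks whether the risk difference varies with the moderator. A Cox model asks whether the hazard ratio varies. These are different hypotheses, and the plan's three labels can change with the scale.

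The decision rules differ too. The regression procedure looks at main effects before it looks at the interaction; the Cox procedure does not. A moderator that reverses the effect tends to cancel the average effect of arm, so a main-effect requirement works against the antagonistic category that the plan sets out to find.

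At stake are the trial's statements about for whom the intervention works. With two unranked procedures, either result could be reported as the planned one.

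**Working it through.** **Inputs.** From the plan: "115 participants were randomized at the time of enrollment following completion of the baseline survey"; 1:1 allocation; two-sided 0.05. The plan gives no screening rates by arm or moderator level and no power figure for moderation, so there is no figure to reproduce. All rates below are assumptions, written as control to intervention at the two levels of a binary moderator.

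**Step 1: scale.** RD = pT − pC. HR = ln(1 − pT)/ln(1 − pC), under proportional hazards with complete 12-month follow-up.

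| Assumed rates | RD (points) | HR |
|---|---|---|
| 10 to 25%; 50 to 70% | 15; 20 | 2.73; 1.74 |
| 20 to 40%; 60 to 80% | 20; 20 | 2.29; 1.76 |
| 20 to 36%; 60 to 84% | 16; 24 | 2.00; 2.00 |
| 25 to 40%; 35 to 50% | 15; 15 | 1.78; 1.61 |

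For the first row, ln(0.75)/ln(0.90) = 2.73 and ln(0.30)/ln(0.50) = 1.74. The same rates are *enhancing* on the difference scale and *buffering* on the hazard scale. In the second and third rows one scale shows no interaction and the other does. In the fourth, with control rates closer together, the divergence is small.

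**Step 2: do significance verdicts differ at this size?** Simulation with 115 participants, a moderator split about 50:50, exponential times and censoring at 12 months, comparing the linear interaction test with the Cox interaction test:

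- Second and third rows: each test significant in roughly 4–7% of trials; verdicts differ in about 5–6%.
- First row: verdicts differ in about 7%, and the estimated interactions have opposite signs in 35%.
- Extreme rates, 20 to 20% and 40 to 90%: linear significant in 90%, Cox in 58%, discordant in 32%.

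**Step 3: the main-effect check, read as a gate.** Assume a true reversal, 20 to 60% at one level and 60 to 30% at the other.

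- Average arm effect: (40 − 30)/2 = 5 points. Average moderator effect: 45% − 40% = 5 points.
- Standard error of each: √[0.425 × 0.575 × (1/57 + 1/58)] = 0.092. Five points is 0.54 standard errors, so the chance of significance is about 8% each, and about 0.08 × 0.08 = 0.6% for both.
- Interaction: 40 − (−30) = 70 points. With 115/4 = 28.75 per cell, its standard error is √[(0.16 + 0.24 + 0.24 + 0.21)/28.75] = 0.172, so z = 4.07.

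In simulation the interaction was significant in about 97% of trials, by the linear test and by Cox alike. With the main-effect checks required, under 1% were declared.

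The gate also matters without a reversal. For 30 to 90% and 60 to 80%, the two interaction tests alone disagree in 10% of trials. With the checks added, the regression procedure declares moderation in 20%, Cox in 75%, and they disagree in 57%.

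**Step 4: R² change.** When the interaction has one degree of freedom, the F test of R² change and the t test of the interaction term give the same p-value. Requiring both adds nothing.

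**The case against.** The strongest reply is that the moderator paragraph is a general framework and the last paragraph is its application to the primary outcome. The first never uses the word linear and never names Y, and the Study Protocol section lists knowledge and self-efficacy as secondary outcomes, for which R² is natural. On that reading nothing conflicts. This stands in part: that a yes/no outcome is to be fitted by linear regression is an inference. It is a strong one, because R², R² change, standardizing every variable and speaking of an occurrence all point that way, but the text does not state it. Cox also models time to screening, so the two procedures differ in the form of the outcome as well as the scale.

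A reader might go further in three ways that the documents do not support.

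- That the two methods will commonly contradict each other. At moderate assumed rates they usually agree, mostly because neither is significant.
- That the plan breaks its own normality requirement here. That requirement is stated for the mediation regressions; the moderator text follows separately.
- That logistic regression is the one right answer. The odds ratio is a third scale: the equal-HR rates of 20 to 36% and 60 to 84% give odds ratios of 2.25 and 3.50. The choice of scale is a judgement; what is needed is to make it and state it.

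Finally, the text does not say outright that a failed main-effect check stops the procedure. Step 3 holds only if it does.

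**Conclusion.** The concern holds as a lack of ranking and an unsound decision rule in the secondary analyses. The plan leaves two moderation procedures that differ in scale and rule, and its labels can reverse between them. That follows from the formulas and needs no particular rates; the percentages do depend on the assumed rates, the 50:50 moderator split and complete follow-up.

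The practical size is uneven. Disagreement from scale alone is small at moderate rates, about 5–6% of trials, and reaches 32% at an extreme. Disagreement from the main-effect checks, if they act as a gate, can be near total: about 97% detection falls to under 1% for the reversal assumed here. The primary chi-square comparison of arms does not depend on any of this.

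**What to change.** For screening by 12 months:

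1. Name one primary moderation model and its effect scale. Either the Cox model of the section's last paragraph or the logistic model that the plan already uses for covariates would serve.
2. Judge moderation by the arm-by-moderator interaction term and its 95% CI alone. Drop the requirement for significant main effects and for a significant R² change.
3. Report risk differences by moderator level beside it. The plan's own effectiveness criterion, "at least 15% higher than that in the control arm", compares proportions, so readers will look for them, and they make any dependence on scale visible.
4. Label every other moderation model and time point as a sensitivity analysis.
5. Confine R²-based hierarchical regression to the continuous knowledge and self-efficacy scores, and say so.

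The cost is SAP wording only, with no new data. The downside is that moderation is then declared on one stated scale, and a pattern visible only on another is supportive evidence at most.
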